10.3 Interim analyses

We plan to conduct three interim analyses (at 50%, 65% and 80% sample size), to assess efficacy of the primary outcome. These formal interim analyses allow us statistically controlled opportunities to stop for either overwhelming evidence of benefit (dexamethasone works) or for futility (given the size and direction of the treatment effect at the interim analysis, there is no realistic possibility of a statistically significant benefit being demonstrated if the study continues). The study can of course stop at any time for safety concerns.

10.4 Health Economic Evaluation

Full details of these analyses will be specified in a comprehensive Health Economic Analysis Plan (HEAP), authored by the study health economist(s), and signed off by the PI prior to analysis, however the following section offers an overview for ease of reference:

To maximise UK policy relevance, health economic analysis will follow NICE reference case recommendations⁴⁷ including: Adoption of an NHS and PSS costing perspective for primary analyses; cost-utility approach (results in terms of incremental cost per quality adjusted life year (QALY)); discount rate of 3.5% for both costs and QALYs; and the use of probabilistic sensitivity analysis (PSA) to generate cost effectiveness acceptability curves (CEACs).⁴⁸

A decision analytic model will be developed during the early phases of the trial utilising Markov chain methodology and based around recommendations from Soares et al⁴⁹. This is anticipated to take the form of a simple Alive/Dead partitioned survival curve model based on survival curve data from the main trial, though other options will be explored. Survival for each trial arm will be extrapolated over 1, 3, and 5 year, and lifetime horizons, with sensitivity analysis of assumed curve trajectory using common distributional assumptions (such as Weibull, Exponential, Gompertz, or log-Normal).

The systematic review by Soares et al⁴⁹ will be topped up to date of analysis to identify any subsequent studies. The results of the review and trial data will then be used to parameterise the model, applying costs based on standard UK price weights and health utilities based by preference on EQ-5D index scores where available, to the predicted survival for each trial arm. It may be necessary for targeted non-systematic reviews to be used to search for any otherwise unsourced parameters, though this is not anticipated.

Results of the cost-effectiveness analysis will be reported in a Bayesian format with no formal hypothesis testing, using a method of moments approach⁴⁸. Incremental cost effectiveness ratios (ICERs) in terms of cost per QALY will be presented and compared to established UK thresholds. [REF] Uncertainty will be presented in the form of PSA using cost effectiveness acceptability curves (CEACs) [REF] with deterministic sensitivity analysis around key assumptions or where a probabilistic approach would be inappropriate.

11. PHARMACOVIGILANCE

The Investigator is responsible for the detection and documentation of events meeting the criteria and definitions detailed below.

Full details of contraindications and side effects that have been reported following administration of the IMP can be found in the relevant Summary of Product Characteristics (SPC) Booklet.

Participants will be instructed to contact their Investigator at any time after consenting to join the trial if any symptoms develop. Adverse events (AE) related to the participant's critical

condition will not be collected. AE related to the side effects of dexamethasone will also not be collected (hyperglycemia, muscle weakness) during the participant's stay in ICU or for 21days as these events are common in critically ill patients, irrespective of whether they got dexamethasone treatment or not. Further detail on this can be found in Section 11.3.2.

11.1 DEFINITIONS

An **adverse event** (AE) is any untoward medical occurrence in a clinical trial participant which does not necessarily have a causal relationship with an investigational medicinal product (IMP). An **adverse reaction** (AR) is any untoward and unintended response to an IMP which is related to any dose administered to that participant.

A serious adverse event (SAE), serious adverse reaction (SAR). Any AE or AR that at any dose:

- results in death of the clinical trial participant
- is life threatening*
- requires in-patient hospitalisation** or prolongation of existing hospitalisation
- results in persistent or significant disability or incapacity
- consists of a congenital anomaly or birth defect
- results in any other significant medical event not meeting the criteria above.

*Life-threatening in the definition of an SAE or SAR refers to an event where the participant was at risk of death at the time of the event. It does not refer to an event which hypothetically might have caused death if it were more severe.

**Any hospitalisation that was planned prior to enrolment will not meet SAE criteria. Any hospitalisation that is planned post enrolment will meet the SAE criteria.

A suspected unexpected serious adverse reaction (SUSAR) is any AR that is classified as serious and is suspected to be related to the IMP, that it is not consistent with the information about the IMP in the Summary of Product Characteristics (SPC) booklet or Investigators Brochure.

11.2 IDENTIFYING AES AND SAES

Aes and SAEs will be recorded from the time a participant signs the consent form until 21 days post randomisation, or death or discharge from ICU, whichever occurs earlier.

Aes and SAEs will be identified by research nurses through review of the participant's medical notes (this includes daily charts, laboratory results and other investigations undertaken as part of routine medical care).

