Severe ARDS patients have a median (inter-quartile range (IQR)) duration of mechanical ventilation of 9 (4-16) days, ICU length of stay of (LOS) of 11 (5-19) and hospital LOS of 16 (6-31) days⁴. Further, patients with ARDS utilise considerable ICU/hospital capacity and cost (Cost per NHS ICU bed-day = £1932; ward= £413; mean estimated cost of ICU stay based on a UK RCT involving ARDS patients⁷ was £26,857 (95 % CI £25,222–£28,491))⁸. Given the long-term sequalae described above, ARDS survivors continue to need primary care contact and ongoing rehabilitation in the community. The mean societal cost at 1 year exceeds £40K, and the total societal cost divided by the number of 1-year survivors is estimated to exceed £90K⁷.

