1.2 RATIONALE FOR STUDY

1.2.1 Justification of the trial

We recently conducted a systematic review to understand the up-to-date landscape of randomised clinical trials (RCTs) in ARDS¹¹. Despite 50 years of research, there are no recommended pharmacological therapies for all-cause ARDS¹².

Glucocorticoids are potent anti-inflammatory drugs, with a good risk benefit profile, and have therefore been tested previously in randomised clinical trials involving ARDS patients. The clinical effectiveness of glucocorticoids in all-cause ARDS, described in section 1.2.3 (i.e., ARDS 'not due to COVID-19') remains uncertain⁹.

DEXA-ARDS¹³, a multicentre RCT conducted in 17 ICUs in Spain, tested a 20 mg starting dose of dexamethasone (as dexamethasone sodium phosphate) in moderate-to-severe ARDS¹, i.e., three times higher than the dose shown to be effective in COVID-19¹⁴. It is important to note the following challenges about DEXA-ARDS RCT before accepting the conclusion that dexamethasone 20mg may benefit patients with all-cause ARDS¹³. The DEXA-ARDS trial stopped early after enrolling 88% of the planned sample size of 314 patients. The trial was powered for the primary outcome of ventilator-free days at 28 days. This short-term primary outcome does not capture the risk of delayed clinical deterioration requiring reintubation at ~180 days seen in the LaSRS Trial¹⁵. The potential long-term safety of glucocorticoid therapy was not reported in DEXA-ARDS trial, a clinically important evidence gap. It is also plausible that usual care provided in the NHS may differ from Spanish usual health care, as outcomes from critical illness are different between the two countries¹⁶.

Furthermore, there are safety concerns due to paucity of RCT data on the short-term as well as the longer-term adverse effects of short course glucocorticoids in this population 9.17. This clinical uncertainty of benefit and risk of harm is reflected in the current UK guidelines for ARDS management 19: 'The use of glucocorticoids in established ARDS should be the subject of a suitably powered, multicentre RCT with long-term follow-up (GRADE: research recommendation 9).'

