Amongst the different regimens reported in the literature, the dosing regimen used in the DEX-ARDS trial appears to be most promising ¹³. DEX-ARDS administered 20mg Dexamethasone sodium phosphate intravenously for days 1-5 and then 10mg intravenously for days 6-10. This study forms the evidence base for this study. The 60-day mortality was 15.3% lower in the dexamethasone group. We reason that dexamethasone at the proposed dose has the highest anti-inflammatory effects compared with other glucocorticoids. Dexamethasone will have pharmacological effects from day 1 that continue beyond the 10-day treatment regime. In pharmacokinetic simulations will maintain a high glucocorticoid

receptor occupancy (trough to peak: 50-90%)²², and will enable once daily dosing due to long biological half-life.

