4.2 INCLUSION CRITERIA

- (a) Provision of informed consent
- (b) Aged 16 years or older
- (c) Admitted to intensive care unit or high dependency unit (ICU)
- (d) Receiving respiratory support via invasive mechanical ventilation or non-invasive ventilatory support (non-invasive ventilatory support includes mask or helmet) or high flow nasal cannula (HFNC) >30L/min
- (e) Within 72 hours of diagnosis of ARDS with moderate to severe hypoxaemia defined as
 - i) a known acute clinical insult or new or worsening respiratory dysfunction (*Note: this includes new deterioration at any time-point during the ICU stay*), and
 - *ii*) opacities on chest imaging not fully explained by effusions, lobar/lung collapse/atelectasis, or nodules, and
 - iii) respiratory failure not fully explained by cardiac failure or fluid overload, and
 - iv) assessment of hypoxaemia done with either PaO₂/FiO₂ ratio <26.7 kPa from arterial blood gases, or SpO₂/FiO₂ <235 with SaO₂<97%

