6.4 DOSE CHANGES

There will be no change to the dosing regimen detailed in 6.3 where patients are in the ICU/HDU. If patients are discharged from ICU/HDU before the 10-day intervention period is complete dexamethasone treatment will stop. If this occurs, participants will continue in the trial and all follow-up data will be collected where possible.

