7. STUDY ASSESSMENTS

7.1 SAFETY ASSESSMENTS

We will capture two key safety events – nosocomial infections, and clinically important upper gastrointestinal bleeding (UGI bleeding). Rationale being these two events are (a) recognised severe side effects of glucocorticoid treatment, and (b) critically ill patients are at risk of these two events. Nosocomial infections will be defined using the proxy of antibiotic free days during critical care stay, by collecting number of days of antibiotic therapy. Clinically important UGI bleeding will be defined as overt GI bleeding (defined as hematemesis, melena, or frank blood in the nasogastric tube or endoscopy confirmed bleeding due to peptic ulceration), needing transfusion of two or more units of packed red blood cells³². For these safety events, we will record the date/time of all events up to day 60 or until ICU stay if earlier than 60-days. Serious adverse events, and adverse events (SAE/AE reporting) will be captured and reported in addition to above outcomes, as per Sponsor guidance.

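### Bleeding and AE/SAE recording ends at ICU/HDU discharge, when dexamethasone also stops, so harms on the ward in early leavers are not systematically captured and the window depends on ICU stay

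*Protocol*

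**What the plan says.** Section 11.2 records AEs and SAEs from consent "until 21 days post randomisation, or death or discharge from ICU, whichever occurs earlier". For the two targeted safety events in section 7.1 (nosocomial infection and clinically important UGI bleeding), "we will record the date/time of all events up to day 60 or until ICU stay if earlier than 60-days". The infection proxy is itself defined as "antibiotic free days during critical care stay"; the point below concerns the bleeding and AE/SAE windows.

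Section 6.4 on treatment: "If patients are discharged from ICU/HDU before the 10-day intervention period is complete dexamethasone treatment will stop". Section 5.5.2 agrees. Section 4.2 uses one label for both unit types ("Admitted to intensive care unit or high dependency unit (ICU"), and section 7.2 also counts HDU as ICU. ICU discharge in 11.2 and the treatment stop in 6.4 are therefore the same event for anyone who leaves before day 10.

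Two statements in the background bear on this. Section 1.2.3: "Dexamethasone will have pharmacological effects from day 1 that continue beyond the 10-day treatment regime". Section 1.2.1: "The potential long-term safety of glucocorticoid therapy was not reported in DEXA-ARDS trial, a clinically important evidence gap"; the same section also points to scarce trial data on short-term harms.

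Table 3 marks AE/SAE recording on day 1, days 2–5 and days 6–10 only, with nothing under the ICU-stay column.

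**The concern.** There are two separate consequences.

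1. **Missed events.** A patient who leaves ICU/HDU before day 10 has no off-drug period under systematic AE/SAE or bleed recording, although the protocol expects the drug to go on acting after the last dose. A transfused bleed on the ward a few days later falls outside both windows. No analysis plan can recover events that sites were not asked to collect. Section 11.3.2 already exempts known dexamethasone side effects from AE recording, so the bleeding measure carries more of the safety assessment than usual.

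2. **A window that treatment can change.** ICU stay is a secondary endpoint in Table 1, and the lay summary gives less extended ICU care as an aim. If one arm leaves ICU earlier, it is watched for less time, and crude proportions with an event are not compared over equal follow-up. Discharge timing is also decided by staff who know the allocation, since the trial is open label.

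At stake is the comparison of harms. The primary mortality analysis is not affected.

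**Working it through.** The protocol gives no figure for bleeding risk or for the effect of truncation, so there is none to reproduce. The check has three steps.

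**Step 1. Which limit usually closes the window?** For severe ARDS, section 1.1.1 gives "ICU length of stay of (LOS) of 11 (5-19") days, as median and interquartile range. A quarter of stays end by day 5 and half by day 11, so between 25% and 50% end before day 10. Three distributions fitted to the three quartiles give:

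| Fit | Fitted quartiles (days) | Stay under 10 days | Stay under 21 days |
|---|---|---|---|
| Lognormal | 5.6, 10.4, 19.2 | 48% | 78% |
| Weibull | 5.2, 10.8, 19.1 | 47% | 79% |
| Gamma | 5.3, 10.7, 19.1 | 47% | 79% |

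These include stays that end in death, which lose no follow-up. ICU exit or death, not day 21, usually closes the AE window.

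**Step 2. Observed risk ratio under a truncated window.** Let L be ICU stay, c the cap (21 or 60 days), h the daily bleeding hazard, s the ratio of ICU stay on dexamethasone to control, and HR the true hazard ratio.

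- Control risk observed = 1 − E[exp(−h·min(L, c))]
- Dexamethasone risk observed = 1 − E[exp(−h·HR·min(sL, c))]

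Assumed, because the protocol gives neither: h = 0.05/60 per day (about 5% over 60 days), constant, and s = 0.9, 0.8 or 0.7. For rare events the ratio is close to HR × E[min(sL, c)] / E[min(L, c)], so it hardly depends on h. The range in each cell is across the three fits.

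| True HR | ICU stay shorter by | Observed ratio, 60-day cap | Observed ratio, 21-day cap |
|---|---|---|---|
| 1.00 | 10% | 0.90–0.91 | 0.94 |
| 1.00 | 20% | 0.80–0.82 | 0.86–0.87 |
| 1.00 | 30% | 0.70–0.72 | 0.78–0.79 |
| 1.25 | 20% | 1.00–1.02 | 1.08 |
| 1.25 | 30% | 0.88–0.90 | 0.97–0.99 |

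Example (Weibull, 60-day cap, 20% shorter stay, HR 1): 0.0090 / 0.0112 = 0.80. With about 854 per arm this is 854 × 0.0112 = 9.6 against 854 × 0.0090 = 7.7 recorded bleeds. The difference of 1.9 compares with a Poisson standard error of √(9.6 + 7.7) = 4.2. At this assumed rate the distortion alone would not produce a clear false signal, but it could cancel a true excess of 25%.

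With one fixed window in both arms the ratio returns to about its true value (1.00 or 1.25), ignoring death.

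**Step 3. Would hospital discharge do instead?** Section 1.1.1 gives hospital stay in the same cohort as median 16 (6–31) days. Half of stays end by day 16, before day 21, and three quarters by day 31, before day 60. Ending at hospital discharge would observe more time but would still truncate, and hospital stay is also a secondary endpoint.

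**The case against.** The strongest case on the other side has five parts.

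- **Follow-up does not end at ICU discharge.** A reader might infer that early leavers have no post-treatment safety follow-up at all. The protocol does not support that. Mortality runs to day 180, reintubation to day 180 or hospital discharge, and rehospitalisation and health service use are collected. Delayed reintubation is the specific late harm raised in section 1.2.1. Patients still in ICU after day 10 do have off-drug recording. This stands, but these items are effectiveness or economic outcomes and do not identify a non-fatal ward bleed.
- **Ward events could still be reported.** Section 11 tells participants to contact the investigator at any time, the duty in section 11.6 starts when the investigator becomes aware of an SAE, and section 11.3.2 keeps trial-related deaths recordable. This stands in part: such events are not barred, but the active notes review of section 11.2 has stopped.
- **No analysis of counts per arm is stated.** Section 10.2 says only that safety data will be described. Dates of the targeted safety events and ICU stay are collected, so rates per day at risk are possible, and that choice belongs to the SAP. This stands for the bias. It does not answer the missed events.
- **The direction is open.** A reader might infer that dexamethasone will be made to look safer. The protocol does not show this. It states no expected shortening of stay, and it plans for 8% fewer deaths; since death closes the window, preventing deaths could lengthen observation on dexamethasone.
- **Confining collection to critical care was deliberate.** The drug is licensed, the trial is Type A risk-adapted, and the two events were chosen because critically ill patients are prone to them. That explains the choice, but sits badly with the protocol's own statements on lasting drug effect and scarce harm data.

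**Conclusion.** The point holds in this form. For patients who leave ICU/HDU before day 10, systematic AE/SAE and UGI-bleed recording ends when dexamethasone ends, so non-fatal harms on the ward are not systematically captured. This follows from the text and needs no assumption.

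The second part is conditional. Crude event proportions would be biased in favour of whichever arm leaves ICU earlier, by roughly 13–20% for a 20% shorter stay, depending on the cap. That size rests on an assumed shortening, a constant and equal hazard, and stay figures for severe ARDS only, which are not stated to run from randomisation. If bleeding risk is concentrated early in critical care, both the distortion and the number of missed ward events would be smaller.

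This is a worthwhile improvement to safety collection. It does not threaten the primary outcome or the sample size of 1708.

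**What to change.** - In sections 11.2 and 7.1, remove ICU discharge as an end point. Record reportable AEs/SAEs to day 21 and UGI bleeds, as defined in 7.1, to day 60 in both arms, in ICU or on the ward, by notes review. The list of events exempt under section 11.3.2 need not change.
- If collection must end at hospital discharge, say so, state that a smaller treatment-dependent truncation remains, and report event rates per day at risk alongside proportions.
- Reconcile Table 3, which marks AE/SAE recording only through days 6–10, with the 21-day limit in section 11.2.

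The cost is a protocol amendment, plus modest ward chart review and data entry for patients who leave ICU early. Sites already follow participants to hospital discharge for reintubation and hospital stay. A bleed needing at least two units of red cells should be readily found in ward records. Treatment and sample size are unchanged.

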11.3 RECORDING AES AND SAES

When an AE/SAE occurs, it is the responsibility of the Investigator, or another suitably qualified physician in the research team who is delegated to record and report Aes/SAEs, to review all documentation (e.g., hospital notes, laboratory and diagnostic reports) related to the event. The Investigator will then record all relevant information in the eCRF/AE log and on the SAE form (if the AE meets the criteria of serious).

Information to be collected includes dose, type of event, onset date, Investigator assessment of severity and causality, date of resolution as well as treatment required, investigations needed and outcome.

11.3.1 Pre-existing Medical Conditions

Pre-existing medical conditions (i.e., existed prior to informed consent) should be recorded as medical history and only recorded as adverse events if medically judged to have worsened during the study.

11.3.2 Aes and SAEs that do not require recording in the CRF

The very nature of critical illness is that many patients' illnesses will worsen before improving, and one in three patients die. Therefore, GuARDS participants may have events that meet the

clinical trial definition of an AE or SAE, but in this patient population they are expected features of critical illness requiring ICU care.

Aes and SAEs that are considered consistent with the expected course of patient's critical illness do not require recording or reporting unless the Principal Investigator (or delegate) considers they may be related to participation in the trial.

These include, but are not limited to:

- complications of ICU procedures
- requirement for further interventions (e.g., surgery) related to the presenting diagnosis.
- reactions to co-prescribed medications
- Known side effects of dexamethasone (e.g., hyperglycaemia, muscle weakness)

Deaths within 60-days of ARDS diagnosis (either during ICU stay, during hospital stay or after hospital discharge) is expected to occur in around 40% of participants and mortality is included within the primary and secondary outcomes for the trial. Death only needs to be recorded as an AE and/or SAE if the Investigator considers that it relates to participation in the trial.

AEs and SAEs that fall within the categories listed above are anticipated and expected in this group of patients. Therefore, these events will not be recorded as AEs or SAEs on the AE log, SAE form or trial database. Details for these events will be recorded in the medical record in accordance with local practice.

11.3.3 Worsening of the Underlying Condition during the Trial

Medical occurrences or symptoms of deterioration that are expected due to the participant's underlying condition should be recorded in the patient's medical notes and only be recorded as AEs on the AE log if medically judged to have unexpectedly worsened during the study. Events that are consistent with the expected progression of the underlying disease should not be recorded as AEs.

